BACKGROUND AND CURRENT STATUS OF THE STUDY TOPIC

Breast Cancer is the most common tumor in women around the world, and is one of the leading causes of death among women in developed countries (1).

It is an important Public Health problem, since according to the World Health Organization more than a million new cases are diagnosed annually, becoming almost a quarter of malignant tumors in females (2). In the West, it has been shown that one in nine to twelve women will suffer from the disease in her lifetime (3).

Most cases occur in postmenopausal women, and the main age at diagnosis is around 60 years (4).

After the diagnosis of breast cancer, the patient undergoes surgical and / or cancer treatment. Chemotherapy, radiotherapy and hormonal therapy are some of the treatment alternatives, which currently are precisely adapted to the type of tumor seeking a better response and survival (5).

Postmastectomy lymphedema is one of the best-known postsurgical and post-actinic sequelae after breast cancer, with a prevalence of around 20% of mastectomized women (6). The conservative treatment of this health problem is based on Decongestive Physical Therapy and Kinesitherapy (7,8). Pneumatic Multicompartmental Pressotherapy helps reduce the feeling of heaviness and stiffness of edema (9).

In addition to postmastectomy lymphedema, the patient undergoing surgery for breast cancer may present Axillary Web Syndrome (AWS) or superficial lymphatic thrombosis. As described by W.M. Yeung et al. In their systematic review (10), it can appear in the first eight weeks after the operation and usually resolves spontaneously within three months of its appearance (11).

The lymphatic thrombus is clinically manifested as a cord that frequently occurs in the armpit, although it can also appear along the upper limb, elbow crease even reaching the first finger (10, 12, 13). Regarding the diagnosis through imaging tests, nuclear magnetic resonance does not manage to clearly identify the axillary network syndrome, being ultrasound the most reliable method, due to the dynamism that can be applied to the patient's arm while the diagnostic test is being carried out (12, 14).

The axillary network syndrome produces pain when abducting and flexing the shoulder, with the respective loss of functionality and limitation of mobility of the affected upper limb (19).

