According to the American Cancer Society, radiation therapy is applied 3-8 weeks after the operation if chemotherapy is not required. If chemotherapy is used, it is applied 3-4 weeks after completion. It is usually applied 5 days a week from Monday to Friday.

The limitation of mobility often leads to a delay in the application of this useful tool in the oncological therapeutic arsenal to prevent recurrences (20, 21, 22, 23). Hence, the need and importance of this study, where the investigator intend to demonstrate that the evolution times of the lymphatic thrombus can be reduced with assisted passive kinesitherapy and stretching.

At present, there are some publications that show possible alternatives of physiotherapy treatment for lymphatic thromb. Many are interventions with a very small sample (even on a case-by-case basis) (24, 25). Others are observational studies or even studies older than five years. There are some studies that combine manual lymphatic drainage (Vodder method) with physical therapy (strengthening, stretching, soft tissue work) with good results (26).

There is ambiguity in the relationship-association between the appearance of lymphatic thrombosis and lymphedema of the ipsilateral limb. Patients who have developed AWS are 44% more likely to develop postmastectomy lymphedema (27). There are other studies that do not find a relationship between the two (28).

The frequency of the AWS is not clear from the current posts. It depends on the type of surgical intervention, age, BMI (16), the appearance of the postoperative seroma, and even breast reconstruction (17). Thus being the frequency 30% of the operated patients (10, 18).

After reviewing the relevant literature, it should be noted that there are very few studies and therefore little evidence on the treatment of AWS. It is not possible to prescript of a clear treatment in a clinical practice guide for this postsurgical sequela. Most publications highlight the importance and need for more research to determine the etiopathogenesis and useful treatment for this health issue (10, 13).

BIBLIOGRAPHY

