- 41. Bleicher RJ. Timing and Delays in Breast Cancer Evaluation and Treatment. Ann Surg Oncol. 2018 Oct;25(10):2829-2838. doi: 10.1245/s10434-018-6615-2. Epub 2018 Jul 2.
- 42.https://www.cancer.org/es/tratamiento/tratamientos-y-efectos-secundarios/tipos-de-tratamiento/q uimioterapia/como-la-quimioterapia-es-usada-para-tratar-el-cancer.html

OBJECTIVES

GENERAL OBJECTIVES

- I. Determine a preliminary exploration of the magnitude of the effect of a kinesitherapy and stretching intervention for the functional recovery of the upper limb, the recovery of the surgical scar and the improvement of the quality of life in women who have suffered from breast cancer.
- II. Create a scale to objectively classify the axillary thrombus (based on its clinical manifestations).

SPECIFIC OBJECTIVES for general objective I:

- Check the intervention of assisted passive kinesitherapy and stretching for the improvement of the range of joint mobility of the affected limb in the shortest possible time.
- Analyze the reduction of pain and increase of the degree of functionality of the ipsilateral upper limb in patients with AWS after the intervention.
- -Determine the impact of the physiotherapeutic intervention on the quality of life of a mastectomized woman with lymphatic thrombus.
- -Analyse the physiotherapeutic intervention reduction of the time on the evolution of the Superficial Lymphatic Thrombus and the application of Radiotherapy within the terms established in the oncological protocols.

SPECIFIC OBJECTIVES for general objective II:

- Create a scale to objectively classify the axillary thrombus (based on its clinical manifestations).

METHODOLOGY

TYPE OF STUDY

Quasi-experimental, prospective study.

STUDY POPULATION

The study sample is made up of patients undergoing surgery for Breast Cancer who attend the Lymphedema Unit of the A.G.S. Campo de Gibraltar Oeste presenting Lymphatic Thrombus after the operation, the recruitment period being from December 2021 to December 2023.

CALCULATION OF SAMPLE SIZE

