To calculate the sample size, the prevalence of axillary network syndrome (AWS) described in the scientific literature was taken into account. It affects 30%. The 2020 records for patients who attended the Lymphedema Unit of A.G.S. Campo de Gibraltar Oeste has also been included adding 83 new patients. With these figures, a random sample of 46 individuals in total would be enough to estimate, with a 95% confidence and a precision of +-5 percent units, a population percentage of 10%.

SELECTION CRITERIA

Patients who meet all the inclusion criteria and no exclusion criteria will be included in this study prospectively.

INCLUSION CRITERIA

- Patient over 18 years old.
- Mastectomized patients (either radical or conservative surgery).
- Patient with lymphatic thrombus in the upper limb ipsilateral to the surgical intervention.

EXCLUSION CRITERIA

- Significant psychological alterations that would prevent the retrieval of the information necessary for the investigation.
- Significant neurological alterations that would prevent the retrieval of the information necessary for the investigation.
- Patients in a situation of legal dispute that would affect their intervention in this study.
- Metastasis not treated with chemotherapy treatment.

WITHDRAWAL CRITERIA

- Withdrawal of informed consent from the patient.
- Administrative decision taken by the researchers, promoter or a regulatory authority.
- Mild adverse event.
- Serious, unexpected or clinically relevant adverse event.

VALUATION CRITERIA

Main Variables:

- Mobility of the affected shoulder, measured by goniometry.
- Functionality assessment using the Constant and DASH scale (29,30).

Secondary variables:

Sociodemographic and clinical-surgical variables

- Age
- Marital status: married or in a common-law relationship, widowed, divorced or separated, single.
- Level of completed studies: illiterate, primary studies, secondary studies, university studies.
- Type of residence: in an urban / rural area.

- Children: yes / no.
- Mother after 30 years old: yes /no.
- Smoker: yes /no.
- Type of cancer. Four categories have been assessed: ductal, infiltrating, in situ, Paget's.
- Number of lymph nodes removed.
- Type of surgery (radical-conservative).
- Breast reconstruction (yes / no).
- Radiotherapy (yes / no).
- Time from surgery to the appearance of the Lymphatic Thrombus in days.

Clinical Variables:

- Visual Analog Pain Scale.
- Goniometry of all joints of the affected upper limb.

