- Record of daily performance of lymphedema prevention kinesitherapy since the operation (days per week / duration in minutes / day).
- Approximate time elapsed since breast cancer diagnosis: years. Date format dd / mm / yy will be included, if possible.
- Stage in which the cancer is found, according to the TNM scale.
- Body mass index.
- Creation of a scale to classify the type of lymphatic thrombus (based on its location, length, thickness, pain, functional limitation and whether it is palpable-visible or not).

Result Variables:

- Level of physical activity measured by the International Physical Activity Questionnaire.
- -Quality of life questionnaire EORTC QLQ-BR23

Employment and leisure Variables:

- Employment situation at the time of data collection: Four categories have been assessed: Active / Retired / Unemployed / Home worker.
- Sport practice: yes / no.
- Sport and frequency.

Description of the intervention

15 sessions of Assisted Passive Kinesitherapy are carried out by the physiotherapist. Five days a week, for three weeks. If it is previously referred, the treatment will be finished earlier (the patient must achieve the same ranges of motion and strength as the contralateral limb, together with the remission of pain).

The stretches applied during the sessions will be gentle and maintained, never exceeding a pain grade 5 VAS (moderate pain), once the tension of the cord is reached between 20-30 seconds. A special effort will be made to recover flexion and abduction of the shoulder, bringing the cord to a tolerable tension on the part of the patient.

Friction will be made on the axillary scar to dislodge underlying planes and the subcutaneous tissue of the muscle fascia.

The patient will be trained in active kinesitherapy to prevent lymphedema and activate lymphatic circulation. Also with hygienic-postural measures for the same purpose.

CONTROL GROUP

All the variables and data for each patients are recorded in their clinical history. Goniometric study will be performed of the affected upper limb (shoulder, elbow, wrist). Constant scale, Quick-Dash, the Visual Analog Pain Scale and the International Scale of Physical Activity will also be performed. This assessment will be carried out the patient arrives at our unit and on day 30, 60, 90.

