Barthel Scale: The Barthel index or Barthel scale is an instrument used by social and health professionals for the functional assessment of a patient and to monitor their evolution. In the case of Social Workers, they value the independence or dependence of the person in each of the activities of daily living (ADL), obtaining as a result the level of performance of the person and carrying out a rehabilitative / compensatory intervention and / or maintenance according to the results obtained. Promoting and / or maintaining the independence of the person.

The scale measures the ability of a person to perform 10 activities of daily life, which are considered basic, in this way a quantitative estimate of their degree of independence is obtained. 100 points is the highest score and the best result in the patient's functionality. 0 points is the worst result and shows the worst functional status.

These patients will be instructed in hygienic-postural care and active assisted auto-kinesitherapy to perform daily for 30 minutes. It will be assessed every 30 days (see exercise pictures).

These exercises are explained to the patient to be executed at home.

Exercise 1.- Codman Pendulum exercises.

Exercise 2.- Standing, Affected shoulder flex sliding palm of the hand on the wall up and down. Keep maximum flex during 15 seconds.

Exercise 3.- Seated, Affected shoulder flex. Seated on a wheeled chair, leaning elbow on a table. Shoulder flex sliding chair backwards and forwards.

Lymphedema prevention exercises. (please visit our YouTube channel "Unidad Linfedema Algeciras": https://www.youtube.com/channel/UC2usHZkrmgyDfEsKhBWKrmw

INTERVENTION GROUP

As well as the control group, all the variables and data for each patient will be collected in their medical history. Goniometric study of the affected upper limb will be performed too (shouder-elbow-wrist). Constan scale, Quick- DASH, Visual Scale will also be completed together with Analogue of Pain and the International Scale of Physical Activity. This exploration will also take place during the first session and on the 30th, 60th and 90th day.

These users will arrive at the first diagnosis of the thrombus in our unit,in order to receive manual therapy by the physical therapist. (see therapy pictures).

They will receive 15 sessions of manual therapy the physiotherapist, 5 days a week ,each session being approximately 40 minutes long.

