For all study objectives in which two qualitative variables are related, the non-parametric Chi-square test will be used and, if necessary, the Fisher test will be used (in cases where the absolute frequency of more than 20% of the levels is less than 5 observations). To quantify the possible predisposing factors, the relative risk measures (RR), Odds ratio (OR) and their associated confidence interval will be obtained; Likewise, the sensitivity or specificity will be presented if it is considered necessary.

All analyzes will be accompanied by graphic representations for greater detail. Missing values will be those that are not completed.

All analyzes will be carried out with free R software and the significance level for all hypothesis testing is determined at 0.05.

WORKPLAN

The study will be carried out according to the following schedule:

Development and approval of the Provincial CEIC

OCTOBER 2021

Beginning of the recruitment period and action on the intervention group

DECEMBER 2021

Drafting of results, discussion and conclusions of the project

DECEMBER 2023

According to the schedule set forth, the research project will be completed in a period of 24 months.

The researcher [name] will register the patients, whether they are in the control group or in the intervention group. The physiotherapy intervention will be applied during 12 sessions from Monday to Friday to the selected patients.

The researcher [name] will be in charge of comparing the results with a double-blind system and thus comparing the results of the control group with the intervention group. The researcher [name] will be the methodological advisor in this research.

[name], with the help of [name] and [name] will write the results, discussion and conclusions of the project.

DISSEMINATION AND DISSEMINATION PLAN

- 1. Publication in journals indexed in the Journal Citation Report (JCR), in the field of Oncology and Rehabilitation and Physical Medicine and Physiotherapy.
- 2. Dissemination of results in national and international Congresses of Oncology and Rehabilitation and Physical Medicine and Physiotherapy.
- 3. Dissemination to the public, press releases and explanatory brochures of the project.
- 4. Dissemination on the website of the A.G.S. Campo de Gibraltar West.

ETHICAL ASPECTS OF THE RESEARCH

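### No rule says how a patient enters the control or the intervention group, and no baseline adjustment is planned, so in a self-resolving condition group imbalance could create or hide a treatment difference

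*Combined protocol and SAP*

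**What the plan says.** - **Design.** Type of Study reads "Quasi-experimental, prospective study". Recruitment is at one unit, from December 2021 to December 2023 (Study Population).
- **Assignment.** In the Workplan a researcher "will register the patients, whether they are in the control group or in the intervention group", and then "The physiotherapy intervention will be applied during 12 sessions from Monday to Friday to the selected patients". No section gives randomisation, alternation, a calendar rule, a preference rule or an allocation ratio.
- **Entry.** For the intervention group: "These users will arrive at the first diagnosis of the thrombus in our unit,in order to receive manual therapy by the physical therapist". For the control group: "This assessment will be carried out the patient arrives at our unit and on day 30, 60, 90".
- **Eligibility.** The only criterion about the cord is "Patient with lymphatic thrombus in the upper limb ipsilateral to the surgical intervention". Cord age and severity are not limited.
- **Natural history.** The Background says the condition "usually resolves spontaneously within three months of its appearance (11"; the Abstract agrees.
- **Variables.** The main variables are shoulder goniometry and the Constant and DASH scales. The list includes days from surgery to cord appearance, but not the age of the cord at study entry.
- **Analysis.** Analysis of Results gives summary statistics for quantitative variables, chi-square or Fisher tests for pairs of qualitative variables, and RR and OR with confidence intervals, all at the 0.05 level. It mentions no baseline adjustment, matching or stratification.
- **Aim.** The Background states that "the investigator intend to demonstrate that the evolution times of the lymphatic thrombus can be reduced". General objective I is more modest: a preliminary exploration of the size of the effect.

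**The concern.** A non-randomised comparison can be informative if the reader knows what assigned the patients and the analysis deals with the differences that follow. Here neither is available. Follow-up runs to day 90, about the time in which most cords are expected to clear untreated. A patient whose cord is already several weeks old at entry should therefore reach resolution sooner after entry than one whose cord has just appeared, whatever the treatment. That baseline pain and mobility also carry through to later values is a reasonable assumption, although the documents do not state it.

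If the groups differ on such features, the effect estimate mixes treatment with starting position. This affects the wish to demonstrate a shorter cord duration, and equally the exploratory objective, since a confounded magnitude is a poor guide to the next study.

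**Working it through.** **1. Is there a rule anywhere?** Four expressions might be taken for one.
- The quasi-experimental label discloses that there is no randomisation. It does not say what replaces it.
- The random sample in Calculation of Sample Size concerns estimating a single proportion.
- The double-blind system in the Workplan concerns comparing results.
- The sentence on arrival at first diagnosis describes when intervention patients come in. It does not say why they are not controls.

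None of these assigns patients.

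**2. Would the analysis correct an imbalance?** No. For the main variables, which are quantitative, the plan names summary statistics only and no between-group test. For qualitative outcomes it names unadjusted tests. Cord age at entry is not on the variable list.

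**3. The plan's own figure.** The only related number is the total of 46. It comes from a precision calculation for one proportion (10%, ±5 points, 95% confidence, 83 patients). Those inputs give n0 = 1.96² × 0.10 × 0.90 / 0.05² = 138.3 and, with finite-population correction, 83 × 138.3 / (82 + 138.3) = 52.1, not 46. That is a separate matter. Here 46 serves only to set an assumed equal split of 23 per group.

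**4. Illustration on a continuous outcome.** All inputs are assumed: 23 per group, outcome SD 1, no treatment effect, unadjusted two-sided z-test at 0.05, and a group difference of d SD at baseline in the direction that favours therapy.

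Bias = r × d, where r is the correlation between baseline and day-30 values. SE = √(2/23) = 0.295. False-positive rate = P(|Z + r·d/0.295| > 1.96).

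| r | d = 0.25 | d = 0.50 | d = 0.75 |
|---|---|---|---|
| 0.3 | 5.7% | 8.0% | 11.9% |
| 0.6 | 8.0% | 17.4% | 33.2% |
| 0.8 | 10.4% | 27.4% | 53.0% |

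At r = 0.6 the biases are 0.15, 0.30 and 0.45 SD.

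**5. Illustration on cord age.** This is a simulation of 2,000 trials per setting, again with assumed inputs: 23 per group, no treatment effect, total cord duration with mean 90 days and SD 20 to 30, and control cords about 14 days old at entry. If intervention cords are 14 days older at entry, time from entry to resolution looks 13 to 14 days shorter. A t-test is then significant in 31% to 58% of trials, and a chi-square test on resolution by day 60 in 25% to 44%. With no imbalance, both stay near 5%.

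**6. Direction.** The bias can go either way. Older cords in the intervention group favour therapy when time is counted from entry. If entry at first diagnosis means younger cords in that group, the same mechanism works against therapy.

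**The case against.** The strongest reply is that the plan is open about being quasi-experimental and that its formal objective is exploratory, so asking for randomisation is partly a preference about design. That stands, and it is why the minimum remedy keeps the design. It does not remove the need to state the assignment mechanism or to plan for its consequences.

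A reader might infer from the Workplan that a therapist hand-picks patients by severity or motivation. The documents do not support this. The word *selected* may mean only assigned, or meeting the section headed Selection Criteria, and the English is rough throughout. The text does not say who treats, and with names removed it cannot show whether the person who registers patients also treats them.

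It is also fair to say that the figures rest on assumptions. The z-test is not one the plan names, no correlation is given, and no passage says that pain or mobility is prognostic. The role of cord age is itself an inference from the stated natural history. The figures show what a given imbalance would do, not that one will occur.

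The Workplan's 12 sessions also conflict with the 15 in Description of the intervention and Intervention Group. Those passages must be reconciled, but that is a different point.

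**Conclusion.** The point holds in this form: no allocation rule is stated and no baseline adjustment is planned, in a condition that usually resolves within the follow-up period and with no limit on cord age or severity at entry. Followed as written, the plan leaves the group comparison open to uncorrected confounding in either direction. Under the assumptions shown, an imbalance of 0.25 to 0.75 SD favouring therapy gives a false-positive rate of about 8% to 33% at a correlation of 0.6, and roughly 6% to 53% over correlations of 0.3 to 0.8, against a nominal 5%. It should be corrected. It does not show that selection by severity is intended or that the result will be biased.

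**What to change.** **Minimum, keeping the quasi-experimental design.**
- State in the Workplan a fixed assignment rule that does not depend on the patient's clinical state, and log all eligible patients.
- Record the date of cord appearance, so that cord age at entry is known.
- Compare the groups on goniometry, Constant and DASH by regression adjusted for the day-0 value (already collected in both groups) and cord age at entry.
- Say openly that a calendar-based rule is predictable, so booking or referral could still steer patients, and that residual confounding remains.

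Cost: one extra recorded date and slightly more analysis.

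**Preferred.** Use a 1:1 permuted-block list generated in R, which the plan already uses. It should be held by someone who neither enrols nor treats, with each assignment revealed only after eligibility and the day-0 assessment are complete. Cost: a change of study type, which would plausibly need ethics review and revised patient information, not merely a notification.

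**If neither is done,** describe the group comparison as exploratory and non-causal, in line with general objective I, and drop the language of demonstration from the Background.

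### The workplan calls the comparison double-blind, but patients and therapist cannot be blind in this design and no masked role or coding procedure is described

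*Combined protocol and SAP*

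**What the plan says.** In WORKPLAN, one researcher is to be in charge of "comparing the results with a double-blind system and thus comparing the results of the control group with the intervention group". The same section says that a researcher "will register the patients, whether they are in the control group or in the intervention group". METHODOLOGY gives the design as "Quasi-experimental, prospective study".

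The two arms differ visibly. Under INTERVENTION GROUP, patients come to the unit "in order to receive manual therapy by the physical therapist", and "They will receive 15 sessions of manual therapy the physiotherapist, 5 days a week ,each session being approximately 40 minutes long". The content includes passive stretching of the cord and scar massage. Under CONTROL GROUP, patients are taught hygienic-postural care and "active assisted auto-kinesitherapy to perform daily for 30 minutes", and "These exercises are explained to the patient to be executed at home".

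VALUATION CRITERIA names as main variables "Mobility of the affected shoulder, measured by goniometry", together with the Constant and DASH scales. Both arm sections schedule goniometry, Constant, Quick-DASH, VAS and IPAQ at the first visit and on days 30, 60 and 90. EORTC quality of life is listed among the result variables.

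**The concern.** Double-blind tells a reader that neither the patient nor the people treating or assessing her knew the group. Here the patient knows from the first session, and so does the physiotherapist. If the term reaches the report, readers will give patient-reported gains more credit than the design supports. The dissemination plan foresees indexed journals, congresses and press releases, so the term could travel. It matters more because the study is quasi-experimental: the documents describe no randomisation or allocation concealment, so blinding would be one of the few protections left.

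The term also hides a gap that might be closed. Whoever reads the goniometer and palpates the cord could perhaps be masked, but the plan does not say who that is or what that person knows.

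**Working it through.** The plan gives no figure for this point, so the check sets its sections side by side and counts outcomes by who supplies the data. It rests on the protocol text and Annexes 1 to 6.

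**Step 1: who can be masked.**

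| Role | What the documents say | Can be masked? |
|---|---|---|
| Patient | Sessions of about 40 minutes with a physiotherapist, or exercises at home; no sham or matched contact | No |
| Treating physiotherapist | Delivers the stretching and massage | No |
| Researcher who registers patients | Registers both groups; no masking of group described | Not as described |
| Outcome assessor | Cord presence is judged by an assessor; not stated to be masked or separate from the therapist | Possibly, if a different person |
| Researcher who compares results | Attached to the double-blind phrase; no coding of groups described | Yes, with coded groups |

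The encryption under ETHICAL ASPECTS OF THE RESEARCH protects identifying data. It does not conceal treatment group from anyone.

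**Step 2: scheduled instruments, by source of data.** Of the five scheduled in both arms:

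- wholly patient-reported: Quick-DASH, VAS, IPAQ (3)
- mixed: Constant (1)
- measured: goniometry (1)

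That is 3 of 5 wholly patient-reported. Adding EORTC quality of life makes it 3 + 1 = 4 of 6.

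**Step 3: the Constant score (Annex 1).**

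- Pain: 15 points
- Daily living: 4 + 4 + 2 + 10 = 20 points
- Range of movement: 40 points
- Power: 25 points

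Patient-reported: 15 + 20 = 35. Measured: 40 + 25 = 65. Total: 35 + 65 = 100.

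**Step 4: the three main variables.** DASH is wholly patient-reported (1 of 3). Constant is patient-reported for 35 of 100 points. Goniometry is measured, but by an assessor not stated to be masked. It also records how far the patient moves her own arm on request, so it depends partly on the effort of someone who knows her treatment.

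**The case against.** The strongest reply is that the plan never says in so many words that patients or therapists are blind. The phrase is attached to one researcher's comparison of results, and a masked comparison is feasible. An unfinished editing note in Spanish under INTERVENTION GROUP suggests a rough translation, so loose terminology is plausible. This stands in part: a reader might infer that the plan asserts patient and therapist blinding, and the documents do not go that far. But even on the milder reading the term misdescribes the study, and the plan gives no coding step that would make the comparison masked.

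A second reply concerns the outcomes. A reader might infer that the main results are mostly self-report. By count of instruments most are, but only one of the three main variables is wholly so, and 65 of the 100 Constant points are movement and power. This stands. For the measured outcomes the open question is whether the assessor is masked.

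A third reply is that the first general objective is a preliminary exploration in a declared quasi-experimental study, and that harm arises only if the report repeats the phrase. This limits the consequence but does not justify keeping an undefined term in the plan.

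**Conclusion.** The point holds as a defect of description with a practical gap behind it. The plan names a level of blinding that hands-on therapy against home exercise cannot have. It identifies no masked role and no procedure. Of the five roles above, two at most could be masked.

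The exposure is one main variable in full (DASH), 35 of 100 points of a second (Constant), and VAS, IPAQ and EORTC quality of life among the others. Goniometry, the other 65 Constant points and cord presence depend on an assessor whose masking is not stated.

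Two stronger inferences are not supported:

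- A reader might try to express the defect as an inflated false-positive rate. That would need a split of the 46 patients between groups, a size for the reporting shift, and a test of means. The documents give no allocation ratio and no figure for such a shift, and ANALYSIS OF RESULTS specifies only descriptive statistics for quantitative variables. Nor would correcting the wording change any bias in outcomes reported by unblinded patients.
- A reader might conclude that goniometry should be put ahead of the other main variables. It depends partly on patient effort, and the plan does not rank the main variables. Labelling the self-reported outcomes is enough.

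The conclusion assumes no sham or masked-assessor procedure beyond what the protocol text describes.

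**What to change.** 1. In WORKPLAN, delete the term double-blind and state that patients and the treating physiotherapist are not blind.
2. Have the researcher who compares the results work from a data file with groups coded A and B.
3. Label DASH, VAS, IPAQ, EORTC quality of life and the pain and daily-living parts of Constant as unblinded self-report in the results and conclusions.
4. If a researcher already on the team does not deliver therapy and can take the measurements, have that person do the day-30, 60 and 90 goniometry and cord assessment without being told the group. Otherwise state that the assessor is not masked.

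Items 1 to 3 cost protocol wording and a coded data file. Item 4 needs no extra staff only if such a person exists. The documents do not show this, because they do not make clear which researcher treats and which measures. The downside is that the reported level of blinding becomes less favourable.
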